### **13.2.3 The Hearing Mechanism**

A basic premise underlying TRT and most counseling theory is that understanding a problem lessens the likelihood that individuals will worry about it or catastrophize it. Hence, an explanation of the hearing mechanism and hearing disorders is an important aspect of tinnitus management. In SC, the description of the hearing mechanism, hearing loss, and tinnitus, will be tailored to the individual's current understanding of his or her problem and his or her level of inquisitiveness. A simplified explanation of the anatomy and physiology of the hearing mechanism will be presented as standard. A Study Participant's questions, interest level, and grasp of the information may prompt elaboration. Because SC is patient-driven, the level of explanation should be determined on a case-by-case basis. In SC, the hearing mechanism and hearing problems are reviewed first to facilitate understanding of the Participant's specific hearing test results.

Following, are the basic points to be covered in reviewing the hearing mechanism.

#### Outer Ear:

- The pinna, or auricle, directs sound waves through the ear canal to the eardrum - the tympanic membrane.
- Sound waves impinge upon the eardrum causing it to vibrate.

#### Middle Ear:

- The middle ear is an air-filled cavity just beyond the eardrum that is lined with mucous membrane.
- The middle ear is ventilated via the Eustachian tube.
- On the other side of the eardrum, are three small bones known as the ossicles or the ossicular chain. The three bones are the hammer, anvil, and stirrup, which are also called the malleus, incus, and stapes.

- When sound waves cause the eardrum to vibrate, the vibration is transmitted to these three bones causing a mechanical action that is a leverage system to transmit sound energy into the inner ear.
- When there is a problem associated with the outer or middle ear, the parts of the ear that conduct sound waves, the type of hearing loss is called a conductive hearing loss.
- The most common causes of conductive hearing loss include excess wax in the ear canal, perforated eardrum, middle ear infections, and otosclerosis. Most conductive hearing losses can be successfully treated medically or surgically.

### Inner Ear

- The inner ear consists of two sensory organs: the semicircular canals, which are responsible for balance, equilibrium, and our orientation in space; and the cochlea, which is the sensory organ for hearing.
- The cochlea consists of three fluid filled chambers, the middle one of which contains a long membrane along which are rows and rows of hair cells that protrude from nerves
- The footplate of the stapes, or stirrup, is attached to an opening to the cochlea and when the ossicular chain vibrates, the footplate rocks back and forth, which causes wave motions in the fluids in the inner ear.
- The wave action causes motion along the hair cells to generate an electrical impulse which is transmitted to nerve endings that send the impulse along nerve fibers that combine to form the auditory nerve – VIII cranial nerve - that sends the signal to the brain where it is perceived as sound.
- The hair cells and nerve endings at the outer end are the ones responsible for the perception of high frequency sound. The ones at the far tip perceive low frequency sounds.
- When there is a hearing problem associated with the inner ear or the VIII nerve and pathway to the brain, the loss is called a sensorineural hearing loss.
- The most common causes of sensorineural hearing loss include noise exposure, diseases (e.g., measles, mumps, meningitis, cytomegalovirus (CMV)), ototoxic drugs, aging, skull fracture or other head trauma. The vast majority of sensorineural hearing impairments are permanent.

- Many of these same factors are associated with tinnitus.
- Most theories of tinnitus involve damage to the nerves in the inner ear.

The Study Audiologist will conclude this portion of the session by engaging the Study Participant in a discussion. It is important to ascertain that the participant has understood and assimilated the review. The Study Audiologist will provide complete responses to any questions the participant may have and provide reassurance about his or her condition.

#### **13.2.4 Audiologic/Tinnitus/Hyperacusis Evaluation**

The next step in SC is to review and explain the results of the Study Participant's ATH evaluation. Using copies of the audiogram and results of the patient's ATH evaluation, the objective for the Study Audiologist is to help the patient to understand the nature of his or her hearing status, tinnitus perception and, if present, hyperacusis. Copies of the audiogram and results of the participant's ATH evaluation will be enlarged using a photocopier for easier viewing and explanation. It is particularly important to gauge the Study Participant's ability to understand the terminology and implications of hearing test results and to present this information at a level that is meaningful to him or her.

The Study Audiologist will present the patient's audiometric results and provide an explanation of the hearing sensitivity for each ear. Study Participants will have functionally normal hearing that does not require amplification to benefit daily listening and communication. The Study Audiologist will review the patient's pure tone thresholds at each audiometric frequency and explain the results of speech audiometry. Among the things the Study Audiologist may highlight are asymmetries in the audiometric results and results consistent with specific etiologies (e.g., high-frequency audiometric notches or declining high-frequency hearing sensitivity, typical of the onset of noise induced hearing impairment), and results warranting further evaluation.

Results of the Loudness Discomfort Level (LDL) test are then reviewed. The Study Audiologist describes the test, reviews the Study Participant's test results, and compares his or her findings with results considered to be within normal limits. If hyperacusis is indicated, by a subjective complaint and/or by reduced LDL values, then the Study Audiologist will explain to the Study Participant how the results indicate the presence of a sound tolerance problem.

Next, the Study Audiologist will describe the Tinnitus Pitch Match, emphasizing that the pitch obtained may not be an exact match, but a "snapshot" of the tone or pitch closest to that of the Study Participant's tinnitus. The Study Audiologist will explain that the way tinnitus sound

varies by individual; it may be a hissing, ringing, buzzing, or chirping sound. The Study Audiologist will also explain the Tinnitus Loudness Match, and explain that the loudness of the tinnitus sound is usually only a few decibels above the threshold of hearing identified at the pitch of the tinnitus sound.

As appropriate, the Study Audiologist will briefly review the results of impedance audiometry and otoacoustic emissions tests and explain that these tests help rule out significant hearing problems and/or identify the type of hearing problem.

The Study Audiologist will conclude this portion of the counseling by ensuring that the Study Participant has a good understanding of his or her hearing test results, the stability of his or her hearing over time in the past, and what to watch for in terms of further hearing loss, particularly from further noise exposure.

### **13.2.5 Coping with Tinnitus**

During this portion of the SC session, the Study Audiologist will highlight the effective ways in which the Study Participant has coped with tinnitus in the past and emphasize additional ways in which he or she may try to minimize the impact of his or her tinnitus in the future. This discussion should be tailored to the individual's specific complaints, problem situations, coping strategies used to date, personal preferences, and feasibility. The following points should be considered.

**Environmental Sounds:** Identify the situations in which environmental sound can be utilized to alleviate tinnitus. This should include a demonstration of environmental and bedside sound generators and provision of literature on a variety of available devices with purchasing/ordering information.

**Stress Reduction:** Review the importance of stress reduction/relaxation to minimize the aggravating effects of tinnitus and discuss a variety of relaxation exercise programs including Tai chi, yoga, meditation, progressive muscle relaxation, and visual imagery. If the Study Participant is not aware of such programs, provide appropriate handouts and conduct a short relaxation exercise such as visual imagery or progressive muscle relaxation. The Study Audiologist will also provide information regarding relaxing background sounds (e.g., small water fountains, and environmental sound CDs.

**Sleep Aids:** The Study Audiologist may address sleep issues by reassuring the Study Participant that many people with tinnitus experience sleep problems and that there are many ways in which these problems can be alleviated if not eliminated. The Study Audiologist will review normal sleep patterns, emphasizing that the best sleep is 8 hours of uninterrupted

sleep. The Study Audiologist will also discuss factors that affect sleeping, including stress and emotional upheaval, environmental variables (noise, light, temperature), irregular schedules, jet lag, medications, caffeine, nicotine, and alcohol. The Study Participant will be encouraged to identify the different variables that may play a part in his or her sleep difficulties. If the Study Participant reports significant sleep problems that may be related to his or her tinnitus, or that aggravate his or her tinnitus, the following recommendations are provided:

- During the day, exercise and avoid naps to promote healthy sleep.
- In the evening, avoid stressful activities and strenuous exercise; avoid caffeine, alcohol, large meals, and spicy foods close to bedtime; and go to bed when tired.
- Maintain a consistent sleep-wake pattern, (i.e., get up and go to sleep at the same time every day).
- Optimize sleeping conditions by eliminating distractions such as TV, computer, food/drink); add comfortable mattress, pillow and comforters; darken the bedroom; set temperature between 58° to 68° F.
- Add soothing, low-level background sounds such as music, nature sounds, broadband/white noise, fan, etc.
- A sound device/noise maker that produces a variety of rushing or roaring sounds.
- If sounds bother partner, consider a pillow speaker.
- Practice progressive relaxation exercises and visual imagery if needed.
- Provide literature and resources including [www.soundsleeping.com](http://www.soundsleeping.com)

**Concentration:** If a Study Participant reports that tinnitus interferes with his or her ability to concentrate, the Study Audiologist will explain that concentration affects performance and memory so it is important to enhance concentration skills and learn to ignore the tinnitus. Factors that affect concentration will be reviewed including noise, temperature, distractions, lighting, hunger, fatigue, health, boredom, stress, depression, and tinnitus. To enhance concentration, the Study Audiologist should recommend:

- Adding environmental sound to reduce tinnitus perception.

- Working in shorter spans and taking breaks.
- Optimizing external/environmental conditions to maximize overall comfort.
- Practicing attention shifting exercises (from one object to another, from tinnitus to other sounds, etc.).
- Staying focused by actively participating, taking notes, asking questions, repeating information, and organizing and categorizing important points.

#### **13.2.4 Treatment Recommendations**

The treatment recommendations for each Participant should reflect a summary of the interactive counseling session and a mutual understanding of the Study Participant's concerns, needs, and ability and willingness to engage in relevant treatment options. The recommendations should reflect the Study Participant's engagement in the decision-making process regarding treatment options. A written outline of the recommendations will be presented to each Study Participant based on the summary discussion. The following general recommendations will also be included:

- Avoid loud noises. If exposure to noise is unavoidable, properly fitted earplugs and/or other hearing protection should be used.
- Avoid caffeine, alcohol, aspirin, and other foods, drinks, and drugs that may affect tinnitus.
- Reduce exposure to identified situations that cause or increase stress.
- Initiate activities that lead to relaxation or reduction of tinnitus perception.

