### **13.2.2 Explaining Tinnitus**

The Study Audiologist will then ask the Study Participant if he or she worries about tinnitus and if so, what aspects of it are the most concerning. After listening to the Study Participant's response, the Study Audiologist will explain that there are some basic facts about tinnitus that makes it less worrisome for most individuals who have it. The following points should be covered:

Tinnitus refers to sounds that are perceived in the ear or brain that do not originate outside one's body. Tinnitus may be perceived differently from one person to another or even one time to another (e.g., ringing, buzzing, hissing, chirping, etc.).

- There are several different theories about what triggers tinnitus from a physiologic standpoint. Most theories associate tinnitus sounds with trauma to the nerve endings in the inner ear or somewhere along the pathway to the brain as will be discussed.
- Almost everyone notices such sounds from time to time.
- Ironically, people with hearing loss can be more annoyed by tinnitus because sounds in the world around them are not masking – or drowning out – the tinnitus.
- The vast majority of people who experience tinnitus are not bothered by it.
- Loud noise, certain medications, illness, head trauma, and stress can cause and aggravate tinnitus.
- The tinnitus may get worse, it may stay the same, or it may go away.
- Tinnitus may result from damage to the hearing system and may or may not be associated with measurable hearing loss.
- Tinnitus by itself will **not** damage your hearing.
- Tinnitus is **not** a health threatening condition.
- Many people learn to ignore their tinnitus.
- There is no known or proven medical treatment for tinnitus.
- Tinnitus is very common among military personnel who have been exposed to loud noise.
- Focusing on one's tinnitus can make it more noticeable.
- One can learn to ignore tinnitus just as one ignores the sound of one's own breathing, the hum from a fluorescent light or the refrigerator, or even the ongoing tick-tock of a grandfather's clock.
- Other sounds in the environment make it easier to ignore tinnitus.

The Study Audiologist will discuss these points and answer any questions the Study Participant may have.

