#### **13.3 Conclusion of Initial Counseling Session**

At the conclusion of the SC session, the Study Audiologist will provide a copy of the handouts on tinnitus facts; environmental sound devices, tips for enhancing sleep, relaxation, and concentration, and websites with additional resources. The Study Participant will also be given a copy of his or her hearing test results, and a summary of the agreed upon treatment recommendations. The Study Audiologist will advise the Study Participant that a follow-up visit will be scheduled in approximately one month to monitor treatment progress. The Study Participant will also be told that he or she may contact the Study Audiologist before then if so

desired. The schedule for subsequent evaluation follow-up visits at the Clinical Center is also provided to the Study Participant.

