**(Engagement)**

The following is provided to guide the SC counseling session. Because each patient's complaints and clinical needs determine the specific areas of emphasis, this should be viewed as a minimal or skeleton script from which additions are encouraged to ensure that each patient's specific complaints are acknowledged and addressed as needed. The SOC counseling session should take 1.5 to 2.5 hrs depending on the patient's questions and needs.

**Elicit patient narrative:** My goal is to make it possible for you to cope with tinnitus so it does not have negative effects on your well-being and your life. To do that, it is important that I understand how your tinnitus affects you every day and how you feel about it. So, please tell me all about your tinnitus.

*(Listen actively and paraphrase periodically to communicate your understanding of what the patient is saying. Encourage further disclosure as necessary to obtain a comprehensive perspective of the patient's tinnitus experience and to provide insight into coping strategies used to date. If necessary, elicit additional information by asking for clarification or examples or gently prod by asking, "How do you feel when that happens?" or "What do you generally do when that happens?" For participants who are withdrawn, any of the following questions can be asked to elicit further disclosure: What kinds of things aggravate your tinnitus? What seems to reduce your tinnitus? When is it most noticeable? When is it least noticeable? What is the most bothersome about your tinnitus? How do you react to your tinnitus? What do you do to cope with your tinnitus?*

*\*If tinnitus effects on stress, sleep, and concentration ability have not been mentioned, ask if problems exist in these areas.)*

**Summarize cognitive (thoughts)/affective (feelings) key points in patient's narrative to communicate mutual understanding and empathy:** From what you are saying, I can tell that tinnitus has been interfering in some important aspects of your life... (identify situations) and that you feel (identify emotions cited) as a result.

*(Allow participant to elaborate further as appropriate to clarify and verify your observations and foster mutual understanding of the problems and their extent.)*

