Appendix A, Script for Standard of Care counseling, continued

After we have talked a little bit more about your tinnitus and tinnitus in general, I want to discuss these situations and how you have coped with them some more because I have some suggestions for other things that will help. For now though, is there anything else you would like me to know about your tinnitus?

*(If there is, verify/clarify as needed and allow patient to elaborate, then say....)*

Ok, that's good. That helps me understand your situation better too. We'll discuss that more when we review the different strategies I want you to start using to minimize the effects your tinnitus is having on you.

**Tinnitus Facts:** Do you worry about your tinnitus? What worries you about it?

*(Acknowledge and identify sources of worry.)*

People often have misconceptions about tinnitus that make it more worrisome, so I'd like to review some facts with you to make sure you don't have any unnecessary concerns that make your tinnitus even more stressful.

*(Provide Handout: Key Points about Tinnitus and review.)*

- Tinnitus refers to sounds that you hear that do not originate outside your body.
- It may be a ringing, buzzing, hissing, or chirping sound.
- Tinnitus results from nerve activity in the inner ear.
- It can be triggered by noise, some medications, disease, head trauma, and stress.
- Tinnitus may or may not be associated with hearing loss.
- It will not damage your hearing.
- Tinnitus is not a health threatening condition.
- It may get worse, may stay the same, or it may go away.

---

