**HANDOUT 1: Key Points about Tinnitus****Tinnitus: what it is and what it isn't**

- ◆ Tinnitus refers to sounds that you hear that do not originate outside your body.
- ◆ It may be a ringing, buzzing, hissing, or chirping sound.
- ◆ Tinnitus results from nerve activity in the inner ear.
- ◆ Tinnitus can be caused by noise, some medications, disease, head trauma, and stress.
- ◆ Tinnitus may or may not be associated with hearing loss.
- ◆ It will not damage your hearing.
- ◆ Tinnitus is *not* a health threatening condition.
- ◆ There is no proven medical treatment for tinnitus.
- ◆ It may get worse, may stay the same, or it may go away.

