8. **Start a relaxing bedtime routine.** Do the same things each night to tell your body it's time to wind down. This may include taking a warm bath or shower, reading a book, or listening to soothing music. Relaxing activities done with lowered lights can help ease the transition between wakefulness and sleepiness.
9. **Go to bed when you're tired and turn out the lights.** If you don't fall asleep within 15 to 20 minutes, get up and do something else. Go back to bed when you're tired. Don't agonize over falling asleep. The stress will only prevent sleep.
10. **Use sleeping pills only as a last resort.** Check with your doctor before taking any sleep medications. He or she can make sure the pills won't interact with your other medications or with an existing medical condition. Your doctor can also help you determine the best dosage. If you do take a sleep medication, reduce the dosage gradually when you want to quit, and never mix alcohol and sleeping pills. If you feel sleepy or dizzy during the day, talk to your doctor about changing the dosage or discontinuing the pills.

---

---

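### Standard-of-care outlines must advise avoiding aspirin and other drugs with no prescriber caveat; the only ask-your-doctor advice about a medicine in the SC material shown concerns sleep medication

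*Combined protocol and SAP*

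**What the plan says.** Section 13.2.4, Treatment Recommendations, provides a written outline for each SC participant, based on the summary discussion. Four general recommendations are included whatever the individual plan. One of them reads: "Avoid caffeine, alcohol, aspirin, and other foods, drinks, and drugs that may affect tinnitus".

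The noise item in the same list adds what to do when avoidance fails: "If exposure to noise is unavoidable, properly fitted earplugs and/or other hearing protection should be used". The drug item has no comparable clause.

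Elsewhere, the SC counseling presents medicines as a possible cause of tinnitus:

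- Section 13.2.2: "Loud noise, certain medications, illness, head trauma, and stress can cause and aggravate tinnitus".
- Chapter 13, Appendix A (script, Tinnitus Facts): "It can be triggered by noise, some medications, disease, head trauma, and stress".
- Chapter 13, Appendix C, Handout 1: "Tinnitus can be caused by noise, some medications, disease, head trauma, and stress".

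None of the three names a medicine.

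Referral to a doctor about a medicine appears once in the SC material, in Appendix C, Handout 2, item 10: "Check with your doctor before taking any sleep medications". The same item tells a participant who is drowsy or dizzy by day to speak to the doctor about a different dose or about stopping the sleeping pills.

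**The concern.** A participant who has been told that some medicines cause or worsen tinnitus, and then takes home a sheet advising avoidance of aspirin and of drugs that may affect tinnitus, has to decide alone which medicines are meant. The wording fits an occasional aspirin for a headache. It also fits aspirin or another medicine that a physician has prescribed. The authors supplied a fallback for noise and a doctor referral for sleeping pills, so the lack of either here looks like an oversight. What is at stake is the safety of an individual who changes a needed medicine on the strength of the outline. The statistical comparison is not at stake.

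**Working it through.** No arithmetic beyond a head count applies. The check is a reading of all the SC material shown: the Chapter 13 text, Table 1, the Appendix A script, the Appendix B one-month visit and Handouts 1 to 6 in Appendix C.

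**1. Is the advice mandatory and unqualified?** Yes. Section 13.2.4 adds the general items to every participant's outline. The drug item has no exception for prescribed medicines and no referral.

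**2. Can it reach prescribed medicines?** Yes, on its wording. It ends in an open class of drugs. The inner-ear part of Section 13.2.3 lists ototoxic drugs among causes of hearing loss and says many of the same factors are associated with tinnitus. The three statements quoted above point the same way without naming a product.

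**3. Is there a caveat elsewhere in the SC material?** Only for sleep medication. Handout 2, item 10 covers both starting and changing or stopping sleeping pills. Its advice on stopping is tied to daytime sleepiness or dizziness, and it also describes tapering by a participant who wishes to quit, without naming the doctor in that sentence. Section 13.3 has the sleep tips handed out at the end of the session, whereas Table 1, item 30 makes sleep literature conditional, so this handout might not reach everyone.

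**4. Where is the drug advice delivered?** Only through the outline. Some places in the sleep advice mention caffeine or alcohol, but avoidance of aspirin or of drugs that affect tinnitus is absent from the Appendix A script, the 40 items of Table 1, the one-month instructions, script and checklist, and all six handouts. The one-month visit follows up sound devices, coping strategies and websites, not medicines.

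**5. Do other procedures supply the caveat?**

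| Procedure | What it does | Tells the participant to ask a prescriber first? |
|---|---|---|
| Section 13.3 and the Appendix A closing | Participant may call the audiologist | No |
| Appendix B, one-month script | Invites questions | No |
| Section 14.3.6 | Otolaryngologist completes or reviews the baseline medical history | No |
| Section 18.4.5.2 | Otolaryngologist consults on cases that may need medical evaluation | No |
| Section 14.7.1 | Medication use recorded from month 3 | No |
| Sections 15.1 and 15.2.2 | Adverse events reported | No; acts after the event |

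**6. Ceiling on exposure.** Section 23.2.3 plans 228 participants in three equal groups: 228 / 3 = 76 in SC. At most about 76 outlines would carry the item. The documents give no figure for how many SC participants take a medicine it could cover, so no smaller number is offered.

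**The case against.** The strongest reply is that this is ordinary lifestyle advice. The word is avoid, not stop, and aspirin stands beside caffeine and alcohol, so the natural reading is discretionary use. The section also asks for recommendations shaped by the participant's own needs. The advice is thinly delivered: no scripted or printed text shown tells anyone to avoid aspirin or drugs. The script is open, since "this should be viewed as a minimal or skeleton script from which additions are encouraged", so an audiologist may add a caveat, and a participant with doubts is told that "he or she may contact the Study Audiologist before then". Part 1 of the document, which includes the eligibility chapter, and the SC forms are not shown. Section 14.2.2 mentions the date a medication was last used as an example of data to collect, so medicines may be dealt with there.

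Most of this stands, and it limits the point to a low-priority one. It does not remove it. The permissive reading is likely but not the only one, a caveat that may be added is not one that is required, and each listed route depends on the participant raising the matter or on staff noticing it later.

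A reader might infer more than the documents support, in three ways:

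- **That no SC material tells a participant to consult a doctor before changing a medicine.** Handout 2, item 10 does so for sleeping pills.
- **That SC participants are told to stop prescribed treatment, or will.** The text does not say stop, and the behavior is inferred.
- **That the advice could distort the TQ comparison.** Nothing shown supports that.

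**Conclusion.** The point holds in a narrow form. Section 13.2.4 requires unqualified avoidance advice that can be read as covering prescribed medicines, and the only ask-your-doctor advice about a medicine in the SC material shown concerns sleep medication. The ceiling is about 76 participants; the number truly at risk is unknown and may be small or zero. The conclusion assumes that the outline reproduces the item roughly as written and that neither Part 1 nor the SC forms contain a caveat; neither assumption can be checked from the material available. This is an optional patient-safety improvement in counseling wording. It is not a flaw in the design or the analysis.

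**What to change.** Add one sentence to the drug item in Section 13.2.4: *Do not stop or change any prescribed medicine, including aspirin, without asking your physician.* Placed there, it appears in the written outline wherever the drug advice does. Issue it through a numbered Policy and Procedures Memorandum (Section 19.3.4.8).

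Repeating the sentence at the Summary and Recommendations step of the Appendix A script is optional, because the script does not currently raise drug avoidance. If it is repeated there, add a matching item to Table 1 and to the Standard of Care Checklist (Section 14.6.3), so that delivery is recorded and can be seen in the adherence review of Section 16.5.2.

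The cost is one memorandum and a one-sentence edit, plus a small script and checklist revision if the optional step is taken. No visits or staff are added, and the counseling contrast between the groups is unchanged.
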